4 SELECTION AND WITHDRAWAL OF SUBJECTS

4.1 Inclusion Criteria

Participants must meet all of the following criteria in order to be eligible to participate in the study:

- 1. Male or female of any age, but enrollment of participants <1 year of age at the time of informed consent will occur only once preliminary safety data are available from 5 participants ≥1 and <6 years of age. See Section 3.3 for details.
- 2. Had an allogeneic HCT performed ≥ 21 days and ≤ 1 year prior to randomization.
- 3. Myeloid engraftment confirmed, defined as an absolute neutrophil count ≥500/mm³ for 3 consecutive laboratory values obtained on different days, and platelet count >10,000/mm³ at the time of randomization. Platelet transfusions are permitted.
- 4. Diagnosed with HC based on meeting all of the following criteria:
 - a. Clinical signs and/or symptoms of cystitis, such as dysuria, urinary frequency, urinary urgency, lower abdominal pain or tenderness, and/or bladder pain, tenderness, or spasms.
 - b. Bedi Grade ≥3 hematuria, defined as macroscopic hematuria with visible clots.
 - c. Viruria with ≥1 target virus (ie, BKV, AdV, CMV, HHV-6, JCV, and/or EBV). Randomization of participant may be based on viruria data obtained from either the local or central laboratory.
- 5. At least 1 identified, suitably matched PSL cell line for infusion is available.
- 6. Willing and able to provide written informed consent to participate in the study, or a parent or legal guardian is willing and able to provide written informed consent and the potential pediatric participant is able to provide assent in a manner approved by the Institutional Review Board (IRB)/Independent Ethics Committee (IEC) and local regulations.
- 7. Women of childbearing potential (WOCBP) and men whose sexual partners are WOCBP must agree to use contraception during the study and for a minimum of 90 days after study treatment as detailed in Appendix H; participants must also refrain from donating sperm or eggs during the study and for at least 90 days after treatment completion.
- 8. Has a negative serum pregnancy test for female participants of childbearing potential.

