9.2.1 Analysis of Efficacy

9.2.1.1 Primary Efficacy Endpoint Analysis

The primary endpoint is the time to resolution of macroscopic hematuria in participants with documented BK viruria. Resolution of macroscopic hematuria is defined as resolution to Grade 0 or 1 on the Bedi scale⁴⁷ on 2 consecutive urine assessments \geq 2 days apart without continuous bladder irrigation or nephrostomy tubes; Grade 1 requires confirmation of resolution by urinalysis results of \leq 100 RBCs/HPF. If a participant has nephrostomy tubes that are capped, Bedi assessments may be performed, including for the purpose of assessing for resolution.

The objective is to demonstrate the superiority of PSL therapy to placebo with respect to the time to resolution of macroscopic hematuria.

The primary efficacy analysis will be conducted after all participants have completed 24 weeks of follow up or discontinued from the study. At the primary analysis, the PSL group will be compared to the placebo group in the BK ITT Population using a stratified log-rank test based on the stratification factors at randomization. The study will be considered a success if the one-sided p-value from the stratified log-rank test comparing treatment to control is less than 0.0147 (reduced from 0.025 due to inclusion of an interim analysis based on Pocock method). A supplementary efficacy analysis based on the overall ITT Population will also be conducted. Time to resolution will be calculated from the time of randomization to the date of the first resolution of macroscopic hematuria (see Section 7.1). Participants not observed to achieve resolution will be considered censored at their last follow-up for the primary endpoint. Definitive therapies to stop bladder bleeding, such as cystectomy, bladder vessel embolization, cauterization, application of fibrin "glue" preparations, or formalin instillation are permitted but will be considered treatment failures for the primary endpoint of time to resolution of macroscopic hematuria and will be censored at 24 weeks. The detailed censoring rules will be specified in the SAP.

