3.4 Efficacy Analyses

3.4.1 Primary Efficacy Endpoint

The primary endpoint is the time to resolution of macroscopic hematuria in participants with documented BK viruria. Resolution of macroscopic hematuria is defined as resolution to Grade 0 or 1 on the Bedi scale on 2 consecutive urine assessments \geq 2 days apart without continuous bladder irrigation or nephrostomy tubes that are uncapped; Grade 1 requires confirmation of resolution by urinalysis results of \leq 100 RBCs/HPF. If a participant has nephrostomy tubes that are capped, Bedi assessments may be performed on urine voided through the urethra or a bladder catheter (eg, Foley or suprapubic catheter), including for the purpose of assessing for resolution.

If the Bedi grade at randomization is missing, then the most recent screening Bedi grade will be used if available. If there are no Bedi grades at either randomization or during screening, the participant will be assumed to be eligible. The primary efficacy analysis will be conducted after all participants have completed 24 weeks of follow up or discontinued from the study. At the primary analysis, the PSL group will be compared to the placebo group in the BK ITT Population using a stratified log-rank test adjusting for stratification factors at randomization (derived based on EDC data). The study will be considered a success if the one-sided p-value from the stratified log rank test comparing treatment to control is less than 0.025. A stratified Cox proportional hazards model will be conducted to produce the hazard ratio of the treatment effect.

Time to resolution will be calculated starting from the date of randomization to the date of the first visual urine assessment without macroscopic hematuria (by the Hemostick® visual scale with score of 0 for outpatients; by the Bedi scale with a Grade 0 or 1 for inpatients) will be used, but 2 consecutive Bedi grades of 0 or 1 are required to establish resolution as noted above. If an outpatient does not have a Hemostick score at the time of resolution, the first of the 2 consecutive Bedi grades of 0 or 1 will be used for determining the time to resolution, which is the same approach being applied to inpatients. For inpatients who resolve on the date of hospital discharge, the Bedi grade scored on the discharge date will be used for determining time to resolution if available; if no Bedi grade is available at the time of discharge, then the Hemostick score will be used.

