Participants not observed to achieve resolution will be considered censored at their last study follow up. Definitive therapies to stop bladder bleeding, such as cystectomy, bladder vessel embolization, cauterization, fulguration, or formalin instillation are permitted. If it is given before or on the day of randomization, the participant will be included in the BK ITT analysis assuming a Bedi of 2 or above. If it is given post randomization, it will be considered treatment failure for the primary endpoint of time to resolution of macroscopic hematuria and will be censored at the last follow-up time of any participant. Participants who discontinued early from the study before

achieving resolution will be censored at the time of last follow up. Participants who died or took non-PSL VSTs prior to reaching resolution will be considered treatment failures and censored at the last follow-up time of any participant.

For Bedi assessments where the grade is not evaluable and the participant is receiving continuous bladder irrigation, has nephrostomy tubes that are uncapped, or the urine is visually bloody, macroscopic hematuria is considered unresolved. For all other Bedi assessments where the grade is not evaluable, the grade is considered missing.

The analysis date for a Bedi assessment is the visual assessment date. If there is no visual assessment date, the urine collection date will be used. Otherwise, the visit date will be used. One Bedi assessment will be selected per analysis date. If there are multiple Bedi assessments on the same analysis date, the worst case is selected. If for a visit, there are Bedi assessments with a visual assessment date or urine collection date, assessments with only a visit date will not be selected.

If there are multiple Hemostick scores on the same date, the highest score will be selected.

If the result of the primary efficacy endpoint (ie, time to resolution of macroscopic hematuria) is statistically significant based on the BK ITT Population, a formal hypothesis test will be conducted sequentially of this same endpoint based on the overall ITT Population using a one-sided 0.025 significance level.

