A sensitivity analysis of the primary efficacy endpoint will also be conducted for the BK ITT population, using a Cox proportional hazards model in order to account for additional potential confounders of the treatment effect. In addition, supportive analyses of the primary efficacy endpoint will also be performed based on the BK mITT, BK PP and mITT Populations.

Primary efficacy endpoint in the estimand framework is described as follows:

Statistical category	Estimand: Treatment: Study Treatment (PSL) or Placebo				
	Population: Pediatric and adult participants with virus-associated hemorrhagic cystitis				
	following allogeneic HCT				
	documented E to Grade 0 or visual urine as nephrostomy capped, Bedi resolution.	Endpoint (Variable): Time to resolution of macroscopic hematuria in participants with documented BK viruria. Resolution of macroscopic hematuria is defined as resolution to Grade 0 or 1 on the Bedi scale as assessed by the Investigator on 2 consecutive visual urine assessments ≥2 days apart without continuous bladder irrigation or nephrostomy tubes that are uncapped. If a participant has nephrostomy tubes that are capped, Bedi assessments may be performed, for the purpose of assessing for resolution			
	Population-le	evel summary: Median time to resolution of ma	acroscopic hematuria.		
	Intercurrent e	events (ICE):			
	1. Use o 2. Early	f definitive therapies to stop bladder bleeding discontinuation from the study treatment before	e achieving resolution		
	3. Death	due to any cause before achieving resolution	To before achieving		
	resolu	ition	is before achieving		
	Analysis set	Intercurrent event handling strategy	Population-level summary (Analysis):		
Primary	BK ITT	 Composite strategy: Participants with ICE 1 will be considered treatment failures for the primary endpoint of time to resolution of macroscopic hematuria and will be censored at the last follow- up time of any participant. Treatment policy strategy: Data collected after occurrence of ICE 2 will be used for the primary endpoint. Composite strategy: Participants with ICE 3 will be censored at the last follow-up time of any participants. Composite strategy: Participants with ICE 4 will be considered treatment failures for the primary endpoint of time to resolution of macroscopic hematuria and will be censored at the last follow- up time of any participant. 	Treatment comparison using a stratified log-rank test (by stratification factors at randomization)		

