Sensitivity Analysis	BK ITT	Same as primary	A stratified Cox model including fixed effect terms for randomized treatment assignment, concomitant antiviral use, and concomitant systemic corticosteroid use.		
Supportive 1	BK mITT	Same as primary	Same as primary		
Supportive 2	BK PP	Same as primary	Same as primary		
Supportive 3	mITT	Same as primary	Same as primary		

Subgroup analyses will be conducted for the BK ITT population to compare the primary endpoint by baseline BKV viruria (<10⁷ copies/mL vs \geq 10⁷ copies/mL), demographic characteristics (eg, age group, sex), stratification factors (derived based on EDC data), and use of concomitant antiviral therapies with potential activity against BK virus during the study. Such agents include cidofovir, ciprofloxacin, and leflunomide. The subgroup analysis will also be conducted by the number of HLA matches and class of HLA matches (class I/II/both).

Analysis will be performed excluding participants who did not have a Bedi Grade ≥2 at randomization from the BK ITT and BK mITT.

All the time to event primary efficacy endpoints will be presented using Kaplan-Meier plots. The estimated median time to event with the corresponding 95% confidence intervals will be presented by treatment group.

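### The Bedi grade of 2 or above assumed after definitive bladder therapy before or on the randomization day can defeat the SAP's own check for participants with nothing left to resolve, and its same-day wording conflicts with the failure rule

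*SAP*

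**What the plan says.** SAP 3.4.1 splits definitive bladder therapy (cystectomy, embolization, cauterization, fulguration, formalin) by timing.

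- **Before randomization or on that day:** the participant is kept, "on the day of randomization, the participant will be included in the BK ITT analysis assuming a Bedi of 2 or above". No failure, censoring or exclusion rule is attached.
- **Afterwards:** "If it is given post randomization, it will be considered treatment failure for the primary endpoint of time to resolution of macroscopic hematuria", with censoring at the longest follow-up in the trial.

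For the event itself, "2 consecutive Bedi grades of 0 or 1 are required to establish resolution as noted above". Time runs from randomization, and nothing is conditioned on an earlier procedure.

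Two supportive analyses guard against participants who enter without macroscopic bleeding. One is in SAP 3.4.1: "Analysis will be performed excluding participants who did not have a Bedi Grade ≥2 at randomization from the BK ITT and BK mITT". The other is the BK per-protocol set (SAP 3.2.5), whose list of possible exclusions includes a grade below 2 at randomization.

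The estimand table in SAP 3.4.1 says "Participants with ICE 1 will be considered treatment failures for the primary endpoint", where ICE 1 is use of definitive therapy. Protocol 9.2.1.1 says that such therapies "will be considered treatment failures for the primary endpoint of time to resolution of macroscopic hematuria and will be censored at 24 weeks". Neither sentence sets a timing limit.

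**The concern.** Protocol 4.2 has no exclusion that names prior definitive therapy. Eligibility requires "Bedi Grade ≥3 hematuria, defined as macroscopic hematuria with visible clots" (Protocol 4.1), but that item carries no date, whereas the platelet criterion in the same section is tied to randomization. A participant can therefore qualify at Grade 3, have the bladder cauterized, and be randomized with clear urine. Such a participant reaches two grades of 0 or 1 at the first assessments. That early event comes from the procedure and says nothing about the study treatment.

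Keeping this participant in the primary intention-to-treat analysis is defensible. The difficulty is that the planned check for such cases may not work. Both safeguards are keyed to the grade at randomization, and the SAP supplies an assumed grade that passes them. If a few such cases fell unevenly between arms, no prespecified analysis would show it.

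Separately, a procedure done hours after randomization on the same day falls under the lenient rule, although it is a post-randomization event.

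**Working it through.** **1. What the assumed grade changes**

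| Rule | Depends on Bedi at randomization? | Effect of the assumed grade |
|---|---|---|
| BK ITT membership (SAP 3.2.2) | No: randomized, BKV in urine | None |
| Primary event (SAP 3.4.1) | No: two later grades of 0 or 1 | None |
| Analysis excluding grade below 2 (SAP 3.4.1) | Yes | Keeps the participant in |
| BK per-protocol (SAP 3.2.5) | Yes, within an open list | Keeps the participant in unless another item applies |
| Subgroup, Cox and mITT analyses (SAP 3.4.1) | No visible use | None; prior procedure is not a factor in any of them |

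In the visible text, the assumption can act only on the two filters.

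**2. Same-day boundary.** Take a procedure done after randomization on the randomization day. Under the timing split in SAP 3.4.1 the participant is followed for resolution. Under ICE 1 and Protocol 9.2.1.1 the participant is a failure. SAP 3.1.2 notes that the protocol puts randomization and first dose on the same day, so the procedure could even follow the first infusion.

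**3. Reproducing the stated power.** Inputs from SAP 2.2.3: medians 6 and 12 weeks, exponential; 24 weeks of follow-up; 20% dropout by week 24, exponential; N = 105; one-sided 0.025. The allocation ratio is blacked out; 1:1 is assumed.

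- Hazards: ln2/6 = 0.1155 and ln2/12 = 0.0578. Dropout: −ln(0.8)/24 = 0.0093.
- Event probability = λ/(λ+g) × (1 − exp(−24(λ+g))). PSL: 0.9255 × 0.95 = 0.879. Placebo: 0.8614 × 0.80 = 0.689.
- Events: 105 × (0.879 + 0.689)/2 = 82.3.
- Schoenfeld: Φ(√(82.3 × 0.25) × ln2 − 1.96) = Φ(1.185) = 88.2%. The Freedman form gives 85.7%.

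The SAP states 86.4%, so its figure reproduces within 2 points.

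**4. Size.** The documents do not give the share f whose bleeding a procedure had already stopped. It is assumed equal in both arms, with resolution at 0.1 to 1 week. Unstratified log-rank test, 6,000 simulated trials per cell, 1:1. Cells show power and resolution hazard ratio.

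| f | Counted as resolution | Excluded | Classed as failure |
|---|---|---|---|
| 0 | 87.9%, 2.07 | 88.5%, 2.07 | 87.8%, 2.07 |
| 5% | 84.4%, 1.97 | 87.2%, 2.07 | 77.2%, 1.90 |
| 10% | 79.2%, 1.89 | 84.6%, 2.07 | 68.6%, 1.80 |

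The f = 0 row is one scenario run three times, so its spread is simulation noise. Counted against excluded:

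- f = 5%: 87.2 − 84.4 = 2.8 points.
- f = 10%: 84.6 − 79.2 = 5.4 points.

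The Monte Carlo error of one cell is about √(0.846 × 0.154/6000) = 0.5 points. A separate run of the counted case gave 84.6% and 80.0%, that is, gaps of 2.6 and 4.6. At 2:1, the counted case falls from 83.2% (f = 0) to 73.8% (f = 10%); exclusion was not run at that ratio.

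Medians shorten in both arms. If the share f resolves at once, the median is m × log2(2(1 − f)). At f = 10% this is 6 × 0.848 = 5.1 and 12 × 0.848 = 10.2 weeks.

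**The case against.** The case on the other side is substantial.

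- **The assumed grade creates no primary events.** A reader might infer that it is what turns procedure-stopped bleeding into study resolution. It is not: striking the assumption would leave BK ITT and every primary event unchanged. This stands in full.
- **The full fall in power is not the cost of the rule.** A reader might take 88% to 79% at f = 10% as that cost. The 88% needs 105 unaffected participants. Excluding the affected ones also loses sample, so the fair comparison is the 5-point gap above. Classing them as failures would cost more than counting them.
- **The exclusion analysis may use observed grades.** The SAP does not say whether assumed or observed grade governs there, and it words the assumption for the BK ITT analysis. If the observed grade governs, a participant at Grade 0 or 1 would drop out. This stands as an ambiguity. However, the exclusion analysis is itself a BK ITT analysis, and the assumption has no other visible use. Moreover, SAP 3.4.1 selects the worst grade on a given date, so a participant graded 2 or above before a same-day procedure would stay in even on observed data.
- **Eligibility narrows the scenario.** Grade 3 is required. Randomization follows confirmation of all criteria (Protocol Appendix A, note 21). The investigator may exclude any condition that would disturb endpoint evaluation (Protocol 4.2, item 21). The BK per-protocol list is open and covers major eligibility violations. All this makes f likely small, but none of it names prior definitive therapy.
- **Randomization balances a baseline procedure in expectation.** Dilution is conservative for a superiority claim. This also stands.

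**Conclusion.** The point holds as a defect in the supportive analyses and as an inconsistency at the same-day boundary. The SAP replaces a grade that can be observed with an assumed one. On the plain reading, this disables the check meant to show whether participants without bleeding at entry drive the result. No other planned analysis isolates them.

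The expected direction is toward no difference, with shorter medians in both arms; chance imbalance among 105 participants could favour either arm. If f were 5% or 10%, an analysis counting these participants would have about 3 or 5 points less power than one excluding them. This assumes 1:1 allocation, equal shares by arm and procedure-driven resolution within the first week. The documents support no particular value of f.

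Two stronger readings fail. There is no inflation of Type I error, because the procedure precedes randomization in all but the same-day cases and affects both arms alike in expectation. Nor do the documents settle that every earlier procedure must be a failure: ICE 1 and Protocol 9.2.1.1 are silent on timing, and an intercurrent event is ordinarily one that occurs after randomization. The clear conflict is confined to same-day procedures done after randomization, and those passages must be reconciled.

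**What to change.** In the SAP:

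1. Keep these participants in the primary BK ITT analysis.
2. In the analysis excluding grades below 2 (3.4.1) and in BK per-protocol (3.2.5), use the observed Bedi grade at randomization wherever one exists.
3. Add a version of the exclusion analysis that also drops participants with definitive therapy on the randomization day or within a prespecified window before it. Report their number by arm.
4. State that a procedure documented as done after randomization on the same day is ICE 1. Name a default for same-day procedures whose order is unknown, fixed before any unblinded data are seen. Align the wording of the timing split, the estimand table and Protocol 9.2.1.1.

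The cost is SAP wording and a prior-procedure flag. The present rule already requires procedure dates, and Bedi grading is scheduled at screening. The documents do not show that clock times are collected, which is why item 4 needs a default. The supportive sets become slightly smaller, and the added version will lose some participants whose procedure failed and who were still bleeding. Primary power is not recovered, apart from any effect of reclassifying same-day cases.

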1.3.3 Summary

The available data, including data from the Phase 2 CHARMS study, confirm the feasibility and safety of PSL administered as an "off-the-shelf" product to treat drug-refractory virus-associated disease. Infusion of the cells was well tolerated, including in participants who received multiple infusions. The infused cells expanded in vivo and were associated with meaningful clinical improvement in participants suffering from refractory BKV, AdV, CMV, HHV-6, and EBV reactivation and virus-associated disease.

In the Phase 2 CHARMS study with PSL, approximately 25% of participants received more than 1 cell infusion using a similar cell dose per infusion as will be used in this study. 42 These additional infusions were administered when participants did not respond adequately to their initial cell infusions and were not associated with a safety or tolerability profile that was different than that associated with single infusions. In the current study, only severely affected HC participants (Grades 3 and 4) who are expected to benefit from the planned 2 sequential infusions will be enrolled. Given the multi-viral coverage of PSL, the 2 infusions are also expected to provide enhanced prophylaxis against those target viruses that may be inactive at the time of infusion, but to which the participants remain susceptible as their immune systems reconstitute following HCT.

For additional information related to clinical studies with PSL, see the current IB.

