3.3.3 Demographic and Baseline Characteristics

The following demographic and baseline characteristics will be summarized, but not limited to:

- Age (years) and age group (<12 or ≥12 years; <18 or ≥18 years; <65 or ≥65 years)
- Use of cidofovir within 4 weeks prior to screening or during the screening process
- Sex
- Childbearing potential

- Race
- Ethnicity
- Height (cm)
- Weight (kg)
- Body mass index (BMI) (kg/m²) and BMI group (<30 kg/m², ≥30 kg/m²)
- Primary malignancy/underlying disease for transplant
- Type of transplant
- Participant CMV serostatus
- Blood Type
- Rh Factor
- HLA alleles from the study participant, the allogeneic HCT donor(s), and the VST donor(s) as well as the number of shared alleles among these individuals
- Baseline viral load in plasma (for BKV, AdV, CMV, HHV-6, JCV) or peripheral blood mononuclear cells (PBMCs; for EBV) for all target viruses
- Baseline viral load in urine for all target viruses
- Receipt of donor lymphocyte infusion >21 days prior to randomization

Demographic and baseline characteristics will be summarized with descriptive statistics or counts and percentages of participants as appropriate by treatment group and in total for all analysis populations.

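### The sensitivity Cox model for the primary endpoint names no baseline disease measure, so it cannot show whether chance imbalance in baseline BKV load explains the result

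*SAP*

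**What the plan says.** SAP 3.4.1 plans one sensitivity analysis of the primary endpoint in the BK ITT Population, "using a Cox proportional hazards model in order to account for additional potential confounders of the treatment effect". The estimand table in that section specifies it: "A stratified Cox model including fixed effect terms for randomized treatment assignment, concomitant antiviral use, and concomitant systemic corticosteroid use". Protocol 9.2.1.1 lists the same two drug-use terms, enters the stratification factors as fixed effects, and calls the analysis supportive. Neither document names a baseline disease measure as a covariate.

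Baseline disease data exist:

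- SAP 3.3.3 tabulates "Baseline viral load in urine for all target viruses".
- SAP 3.4.1 plans subgroup analyses "to compare the primary endpoint by baseline BKV viruria", cut at 10^7 copies/mL. The same sentence lists the stratification factors as a separate item.
- Bedi grade is recorded at randomization, with a fallback: "If the Bedi grade at randomization is missing, then the most recent screening Bedi grade will be used if available".

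The stratification factors are redacted in both documents. From SAP 3.1.5 only cidofovir use can be inferred.

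The Cox model does not decide the trial: "The study will be considered a success if the one-sided p-value from the stratified log rank test comparing treatment to control is less than 0.025".

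**The concern.** A model meant to handle confounding in a randomized trial should first carry baseline variables that could differ between arms by chance and that bear on outcome. Here the named covariates are two drug-use terms. Under SAP 3.3.5, concomitant use includes drugs started on or after the first dose, so these terms are not baseline measures of disease.

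The SAP treats viral load as relevant enough for a subgroup cut but does not adjust for it. If the primary result is borderline and the arms differ in baseline viral load, the obvious question is whether that difference explains the result. The planned model cannot answer, and a severity term added after unblinding would be post hoc.

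**Working it through.** **1. The plan's own power.** Inputs from SAP 2.2.3: 105 participants, exponential times with medians of 12 and 6 weeks, 24 weeks of follow-up, 20% exponential dropout, one-sided 0.025, stated power 86.4%. The allocation ratio is redacted, so 1:1 and 2:1 are both shown as assumptions.

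- Hazard λ = ln 2/median: 0.0578 (placebo), 0.1155 (PSL). Dropout hazard c = −ln(0.8)/24 = 0.0093.
- P(event) = λ/(λ+c) × [1 − exp(−24(λ+c))]: placebo 0.8614 × 0.80 = 0.689; PSL 0.9255 × 0.95 = 0.879.
- Events D: 82.3 at 1:1; 85.7 at 2:1.
- Schoenfeld power Φ(√(D·a(1−a))·ln 2 − 1.96), with a the share on PSL: 88.2% at 1:1; 85.6% at 2:1.
- With the futility rule (conditional power below 5%, information fraction assumed 0.5): 86.5% at 1:1; 83.8% at 2:1.

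The stated 86.4% is reproduced at 1:1. It belongs to the log-rank test, and nothing below changes it.

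**2. How likely is imbalance?** For a binary baseline factor with prevalence p, the SD of the arm difference is √(p(1−p)(1/n₁+1/n₀)). At p = 0.5 this is √(0.25 × (1/52 + 1/53)) = 0.098 at 1:1 and √(0.25 × (1/70 + 1/35)) = 0.104 at 2:1. Simulated with p = 0.5 and 0.4 under both ratios, a difference of at least 10 points has a 31–33% chance, and of at least 20 points a 4–5% chance.

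**3. What does it do to the estimate?** To first order, the unadjusted log hazard ratio shifts by imbalance × |ln(factor hazard ratio)|. For a 10-point imbalance:

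- factor hazard ratio 0.5: 0.10 × 0.693 = 0.07, or 10% of the assumed ln 2 = 0.693
- 0.67: 0.10 × 0.400 = 0.04
- 0.8: 0.10 × 0.223 = 0.02

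**4. What does adjustment gain?** The documents give no prognostic strength, so a range is assumed. Each setting has 3,000 simulated trials of 105 participants, medians of 12 and 6 weeks, 20% dropout, and two binary baseline factors (assumed prevalence 50% and 40%) with the same resolution hazard ratio. Cox power at one-sided 0.025, without and with the two factors:

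| Factor hazard ratio (each) | 1:1 without | 1:1 with | 2:1 without | 2:1 with |
|---|---|---|---|---|
| 1.0 | 88.0% | 88.0% | 82.8% | 81.9% |
| 0.8 | 87.0% | 87.2% | 81.5% | 82.7% |
| 0.67 | 83.9% | 86.7% | 77.3% | 81.5% |
| 0.5 | 77.1% | 85.6% | 69.6% | 80.4% |

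The change is about −1 to +1 point for weak factors (0.8–1.0), 3–4 points at 0.67 and 8–11 points at 0.5. The Monte Carlo standard error of each figure, √(P(1−P)/3000), is 0.6 to 0.8 point.

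At 0.5 the mean standard error of the log hazard ratio rises with adjustment, from 0.229 to 0.236 (1:1) and from 0.248 to 0.254 (2:1). The gain comes from less attenuation: the mean log hazard ratio goes from about 0.61 to 0.71.

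Two limits apply. The simulated models contain no strata and no drug-use terms. The treatment hazard ratio is 2 within each factor level, so the arms are not exactly exponential overall once the factors matter. The table compares two Cox models; it does not correct the 86.4%.

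**The case against.** The strongest reply is that the model is not decisive, the strata are hidden and the matter is partly covered elsewhere.

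- **Redaction.** The model is stratified and the factors cannot be read. A reader might infer that baseline hematuria severity is left out. The documents do not support that: Bedi grade or irrigation status may be a stratum. For BKV load, its separate listing in the subgroup sentence suggests it is not one, though that is inference. This part of the objection stands.
- **Not decisive.** A reader might infer that the trial loses power or precision. It does not: success rests on the stratified log-rank test, and the Cox standard error rises slightly with adjustment. This stands in full.
- **Unknown strength.** A reader might infer that viral load is among the strongest predictors of resolution. Neither document says so, and with weak factors the gain is nil. Entry at Bedi Grade 3 or above (Protocol 4.1) may also narrow the spread. Against that, SAP 3.4.1 foresees participants below Grade 2 at randomization who stay in BK ITT. Under SAP 2.3.1, resolution cannot be assessed until continuous irrigation stops, which ties baseline hematuria status to the endpoint.
- **Covered elsewhere.** The baseline table would reveal an imbalance, and the subgroup analysis shows the effect at each load level. Neither gives an overall effect adjusted for viral load, so this answers only part of the point.
- **Coding.** SAP 2.3.1 codes irrigation or uncapped nephrostomy tubes at randomization as Grade 3, some grades will be low or missing, and BKV results may come from local laboratories. These are fair and shape the fix. Protocol Appendix D sends urine from Day 0 onward to the central laboratory, so local values should be the exception.

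**Conclusion.** The point holds in limited form. The model names no baseline disease measure, baseline urine BKV load is available and appears not to be a stratum, and imbalance of a size worth checking is realistic at this sample size. The 10-point case is the fair illustration; a 20-point imbalance is a tail event.

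The benefit is a direct check on chance imbalance and a less attenuated Cox estimate. Its size rests on assumed factor prevalence, prognostic strength and allocation ratio, and could be close to zero. The change is worth making because it is nearly free, not because the primary analysis is at risk.

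**What to change.** Before unblinding, amend the sensitivity row of the estimand table in SAP 3.4.1 to add:

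1. log10 baseline urine BKV load, continuous, using the latest result up to the day of randomization and the central/local laboratory rule of SAP 3.2.2;
2. unless already a stratum, baseline hematuria status with levels that cover everyone: Bedi 2 or below, 3, 4, and on irrigation or with uncapped nephrostomy tubes. Missing grades follow SAP 3.4.1; state the level for a participant with no grade at all, whom the SAP assumes eligible. The irrigation level needs its own derivation because SAP 2.3.1 otherwise merges it with Grade 3.

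Use the same baseline terms in the key secondary Cox model, whose covariates SAP 3.4.2 does not name. Add baseline pain only if it is defined consistently across the BPIC SD and Wong-Baker scales, including participants counted as exceeding mild pain because of pain medication or bladder care.

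The cost is a short SAP edit, one derived variable and no new data. The primary-endpoint model gains up to four degrees of freedom (one for viral load, three for four hematuria levels) against about 80 events. The primary test is unchanged.
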